8.2.3. Electrocardiograms

Standard twelve (12)-Lead ECGs should be collected at times specified in the [Schedule of Activities](#) section of this protocol using an ECG machine that automatically calculates the heart rate and measures PR, QT, and QTc intervals and QRS complex. All scheduled ECGs should be performed after the participant has rested quietly for at least 10 minutes in a supine position. When a meal or snack is scheduled at the same time as an ECG, the ECG measurement must be performed prior to the meal/snack.

TriPLICATE 12-lead ECGs will be obtained approximately 3 minutes (± 1 minute) apart; the average of the triplicate ECG measurements collected at each nominal time point on Day -1 will serve as each participant's time-controlled baseline value. To ensure safety of the participants, a qualified individual at the investigator site will make comparisons to baseline measurements. Additional ECG monitoring will occur if a) the mean value from the triplicate measurements for any postdose QTcF interval is increased by ≥ 30 msec from the baseline and is >450 msec; or b) an absolute QTcF value is ≥ 500 msec for any scheduled ECG. If either of these conditions occurs, then a single ECG measurement must be repeated at least hourly until QTcF values from 2 successive ECGs fall below the threshold value that triggered the repeat measurement.

If a postdose QTcF interval remains ≥ 30 msec from the baseline and is >450 msec; or b) an absolute QTcF value is ≥ 500 msec for any scheduled ECG for greater than 4 hours (or sooner, at the discretion of the investigator), or QTcF intervals get progressively longer, the participant should undergo continuous ECG monitoring. A cardiologist should be consulted if QTcF intervals do not return to less than the criterion listed above after 8 hours of monitoring (or sooner, at the discretion of the investigator).

ECG data will be submitted to a blinded central reader for assessment. The final ECG report from the central reader should be maintained in the participant's source documentation and be the final interpretation of the ECG recording.

In some cases, it may be appropriate to repeat abnormal ECGs to rule out improper lead placement as contributing to the ECG abnormality. It is important that leads be placed in the same positions each time in order to achieve precise ECG recordings. If a machine-read QTcF value is prolonged, as defined above, repeat measurements may not be necessary if a qualified medical provider's interpretation determines that the QTcF values are in the acceptable range.

ECG values of potential clinical concern are listed in [Appendix 7](#).

8.2.4. Clinical Safety Laboratory Assessments

See [Appendix 2](#) for the list of clinical safety laboratory tests to be performed and the [Schedule of Activities](#) for the timing and frequency.

The investigator must review the laboratory report, document this review, and record any clinically relevant changes occurring during the study in the AE section of the CRF. Clinically significant abnormal laboratory findings are those which are not associated with the underlying disease, unless judged by the investigator to be more severe than expected for the participant's condition.

All laboratory tests with values considered clinically significantly abnormal during participation in the study or within 3 days after the last dose of study intervention should be repeated until the values return to normal or baseline or are no longer considered clinically significant by the investigator or medical monitor.

If such values do not return to normal/baseline within a period of time judged reasonable by the investigator, the etiology should be identified and the sponsor notified.

All protocol-required laboratory assessments, as defined in [Appendix 2](#), must be conducted in accordance with the laboratory manual and the [Schedule of Activities](#).

If laboratory values from non-protocol-specified laboratory assessments performed at the institution's local laboratory require a change in participant management or are considered clinically significant by the investigator (eg, SAE or AE or dose modification), then the results must be recorded in the CRF.

Participants may undergo random urine drug testing at the discretion of the investigator. Drug testing conducted prior to dosing must be negative for participants to receive investigational product (exception may be made for medically prescribed benzodiazepines, see [Section 5.2](#)).

8.2.4.1. Fasting Fingerstick Blood Glucose (via Glucometer)

Investigators will monitor fasting fingerstick blood glucose (FSBG) using a glucometer at the times specified in the [Schedule of Activities](#). While the participant is confined to the CRU, FSBG measurements should be taken each morning before breakfast.

FSBG readings will be maintained at the sites in source documents, and only the glucose results from the laboratory will be reported in the study database. The sites may share the FSBG readings with the sponsor for the purpose of dose-escalation decisions, but these data will be stored in the sites' source documents unless related to an AE as described in [Section 8.2.4.2](#) below.

If an FSBG result is ≤ 70 mg/dL, a second FSBG should be obtained to confirm the glucose value, in addition to a venous sample that will be sent to the clinical laboratory for confirmation. If the value from this second FSBG is also ≤ 70 mg/dL, the second value will be recorded as a hypoglycemic AE (see [Section 8.2.4.2](#)). FSBG will continue to be monitored until the glucose value returns to >70 mg/dL. Samples may be taken more frequently if deemed necessary by the investigator. FSBG readings from a glucometer are permitted at any time if the investigator or participant notes symptoms of hypoglycemia.

8.2.4.2. Hypoglycemia Reporting

Hypoglycemia will be assessed and reported in several categories: severe hypoglycemia, documented symptomatic hypoglycemia, asymptomatic hypoglycemia, and probable hypoglycemia.

Severe hypoglycemia: In order to be considered severe hypoglycemia *all* of the following 3 criteria must be met:

1. The participant had 1 of the following:
 - Blood glucose <50 mg/dL; or
 - If blood glucose was not measured, the clinical manifestations were reversed by carbohydrate administration.
2. The participant required the assistance of another person to actively administer carbohydrate, glucagon, or other resuscitative actions.
3. The participant exhibited at least 1 of the following neurological symptoms:
 - Memory loss;
 - Uncontrollable behavior;
 - Irrational behavior;
 - Unusual difficulty in awakening;
 - Suspected seizure;
 - Seizure;
 - Loss of consciousness.

Documented symptomatic hypoglycemia: An event during which typical symptoms of hypoglycemia are accompanied by a measured glucose concentration ≤ 70 mg/dL.

Asymptomatic hypoglycemia: An event not accompanied by typical symptoms of hypoglycemia but with a measured glucose concentration ≤ 70 mg/dL.

Probable symptomatic hypoglycemia: An event, during which typical symptoms of hypoglycemia are not accompanied by a real time glucose determination, but were presumably caused by a plasma glucose concentration ≤ 70 mg/dL. The clinical picture must include prompt resolution with oral carbohydrates, subcutaneous glucagon, or intravenous glucose.

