6.5.5. Rescue Medicine

There is no rescue therapy to reverse adverse events (AEs) observed with PF-07081532; standard medical supportive care must be provided to manage any AEs (see [Section 6.5.3 Management of Nausea and Vomiting](#)).

For medical management of hypoglycemia, the investigator may administer oral carbohydrate, glucagon, or IV glucose according to his or her medical judgment. At a minimum however, treatment or administration of a scheduled meal should be given if glucose falls <60 mg/dL for at least 15 minutes, irrespective of whether the participant exhibits symptoms. Investigators may choose to administer treatment sooner if participants have bothersome symptoms of hypoglycemia along with glucose values of ≤ 70 mg/dL.

No rescue therapy will be provided for hyperglycemia. If a participant has sustained elevated fasting plasma glucose concentrations that are >270 mg/dL on 3 consecutive measurements over 3 days, that participant will be discontinued, and the investigator will recommend further appropriate glycemic treatment according to the local healthcare standards and national guidelines.

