3.1.1.1. Hypoglycemia Monitoring and Reporting

Hypoglycemia AEs will be recorded in the Case Report Form (CRF) on a specific page. Details of when these will be recorded are given in the protocol Section 8.2.4.2.

For programming purposes, the hypoglycemic AE categories are based on the following:

- Severe Hypoglycemia: Severe is checked in the severity criteria of the CRF. This assessment will be made by the PI based on the protocol definition.
- Documented Symptomatic Hypoglycemia: If
 - (1) – Did the participant have symptoms of hypoglycemia? Yes
 - and (2) – Was the blood glucose measured? Yes
 - and result \leq 70 mg/dL on the CRF,
 - but hypoglycemia is not classified as severe.
- Asymptomatic Hypoglycemia: If
 - (1) No
 - and (2) Yes
 - and result \leq 70 mg/dL on the CRF,
 - but hypoglycemia is not classified as severe.
- Probable Symptomatic Hypoglycemia: If
 - (1) Yes and
 - (2) No and
 - (2b) – If blood glucose was not measured, did symptoms resolve when treated with carbohydrate or glucagon? Yes on the CRF,
 - but hypoglycemia is not classified as severe.

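### When no glucose value exists, the severe-hypoglycemia definition counts reversal by carbohydrate but not by glucagon, so the reporting category of an assisted event depends on which permitted agent was used

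*Protocol*

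**What the plan says.** Protocol 8.2.4.2 sets a conjunctive rule: "In order to be considered severe hypoglycemia *all* of the following 3 criteria must be met".

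- **Criterion 1** has two branches. With a measurement it is "Blood glucose <50 mg/dL; or". Without one it is "If blood glucose was not measured, the clinical manifestations were reversed by carbohydrate administration".
- **Criterion 2** concerns help from others: "The participant required the assistance of another person to actively administer carbohydrate, glucagon, or other resuscitative actions".
- **Criterion 3** is neurological: "The participant exhibited at least 1 of the following neurological symptoms". The list includes seizure and loss of consciousness.

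The same section defines probable symptomatic hypoglycemia for events with no real-time glucose value. There the clinical picture must include "prompt resolution with oral carbohydrates, subcutaneous glucagon, or intravenous glucose".

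Protocol 6.5.5 allows glucagon in the trial: "the investigator may administer oral carbohydrate, glucagon, or IV glucose according to his or her medical judgment".

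SAP 3.1.1.1 turns this into programming rules. Severe is a box on the CRF, ticked by the principal investigator on the basis of the protocol definition. Probable symptomatic needs symptoms, no glucose measurement, a yes to "If blood glucose was not measured, did symptoms resolve when treated with carbohydrate or glucagon", and no severe classification. SAP 6.1.1.4 lists hypoglycemic adverse events and summarizes them by category and treatment.

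**The concern.** Section 8.2.4.2 foresees glucagon as the assistance given in a severe event, but does not count recovery after glucagon as evidence for that event when no glucose was measured. It does count such recovery for the probable symptomatic category. Two events alike in assistance, symptoms and missing glucose can therefore fall into different categories because of the agent used.

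Adverse events are part of the primary endpoint (Protocol 3, SAP 2.1), and the hypoglycemia summary is the table in which a reader would look for severe cases. The discrepancy runs one way: it can only take events out of the severe row.

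**Working it through.** The plan states no figure to reproduce, because this is a classification rule. The check applies the rule to one fixed event and varies only what criterion 1 depends on.

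**Fixed features.** Symptoms present, assistance by another person (criterion 2 met), and a seizure or loss of consciousness (criterion 3 met).

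**Rules applied, in the SAP's order.**

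1. Severe if glucose was measured and is below 50 mg/dL, or if it was not measured and carbohydrate reversed the event (Protocol 8.2.4.2).
2. Otherwise documented symptomatic if glucose was measured and is at most 70 mg/dL (SAP 3.1.1.1).
3. Otherwise probable symptomatic if glucose was not measured and symptoms resolved with carbohydrate or glucagon (SAP 3.1.1.1).
4. Otherwise no category.

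The last column repeats the exercise with glucagon added to the unmeasured branch of criterion 1.

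| Glucose | Reversed by | As written | Glucagon added |
|---|---|---|---|
| 45 mg/dL | carbohydrate | severe | severe |
| 45 mg/dL | glucagon | severe | severe |
| 60 mg/dL | glucagon | documented symptomatic | documented symptomatic |
| not measured | carbohydrate | severe | severe |
| not measured | glucagon | **probable symptomatic** | **severe** |
| not measured | other resuscitative actions only | no category | no category |

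One of the six cells changes. A measured value below 50 mg/dL is severe whatever the treatment, so the discrepancy is confined to events with no value that were reversed by glucagon alone.

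**Does the SAP repair it?** No. It defers to the protocol definition for severe, and its resolution question then sends the glucagon case to probable symptomatic. An investigator could still tick severe, but only by departing from the definition that the SAP cites.

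**Illustrative size.** Protocol 9.2 plans 8 active participants per cohort in Parts A and C, and 12 in Part B. If one such event occurred:

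- Parts A and C: 1/8 = 12.5% becomes 0/8. The exact 95% interval for 1/8 is 0.3% to 52.7%. For 0/8 the upper limit is 1 − 0.025^(1/8) = 36.9%.
- Part B: 1/12 = 8.3% becomes 0/12.

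These figures assume that the event happens. The documents give no rate from which to say how likely that is.

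**The case against.** The strongest objection is that the triggering case is close to empty. It needs no glucose value, reversal by glucagon alone, another person's help and a listed neurological symptom, all in one event. Participants are confined to the unit during dosing (Protocol 4.2.2), and fingerstick readings are permitted whenever symptoms are noted (8.2.4.1). Protocol 4.2.4.1 says that the class is not typically associated with hypoglycemia unless given with agents such as insulin or sulfonylureas, which 6.5.4 prohibits. This stands, and it limits the weight of the point. It does not remove it: the protocol chose to write a branch for unmeasured glucose. That branch matters most after discharge, when follow-up continues to at least 28 days after the last dose (4.1) and SAP 3.1.1 still counts events as treatment emergent.

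A reader might infer more than the documents support in four ways.

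- *That the worst events go unreported.* They do not. Hypoglycemic events are listed as well as tabulated (SAP 6.1.1.4), every adverse event receives an intensity rating (Protocol 10.3.3), and convulsions without hospital admission are a named example of a serious event (10.3.2). The escalation rules in 6.6.1 do not use the hypoglycemia category.
- *That anyone unable to swallow drops out of the severe category.* Criterion 1 refers to carbohydrate without limiting it to the oral route. Intravenous glucose, which 6.5.5 also permits, can reasonably be counted as carbohydrate. The clear gap is glucagon.
- *That the SAP holds a competing definition of severe.* It does not. Its question about carbohydrate or glucagon belongs only to probable symptomatic, and criterion 2 names glucagon as help given, not as evidence of reversal. The SAP question is the route by which the event is filed lower.
- *That an assisted event with a recorded 50 to 70 mg/dL is also misfiled.* Its classification follows from an explicit threshold that nothing in the documents contradicts.

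**Conclusion.** The point holds as an internal inconsistency in a reporting definition. With glucose unmeasured, an assisted event with a listed neurological symptom is severe after carbohydrate and probable symptomatic after glucagon, and the SAP passes that result into its summary table. What is wrong is the category label in SAP 6.1.1.4, not the detection or reporting of the event.

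The practical effect should be small. The 1/8 versus 0/8 comparison shows how one event would look in a small cohort; it does not predict that one will occur. The study tests no hypotheses (Protocol 9.1), so no error rate or power figure is affected.

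The conclusion rests on two readings: that glucagon is not carbohydrate administration, which the section itself supports by naming the two separately, and that investigators apply the definition literally, as SAP 3.1.1.1 says they will. If some read it more loosely, the category would vary between investigators, which is also undesirable. Because the inconsistency is plain and almost free to remove, it should be corrected.

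**What to change.** In Protocol 8.2.4.2, severe hypoglycemia, criterion 1, second bullet, reconcile the reversal wording with the agents already named in that section: carbohydrate, understood to include intravenous glucose, or glucagon. The category then no longer depends on which permitted agent was used. This concerns how events are classified for reporting; it makes no recommendation on how hypoglycemia should be treated.

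The SAP rule for severe needs no separate edit, because it follows the protocol definition, and its resolution question already covers both agents. The change does not reach an unmeasured event reversed only by other resuscitative actions, which still falls into no category.

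The cost is a few words in the protocol. The severe count may be slightly less favourable.

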8.3. Adverse Events and Serious Adverse Events

The definitions of an AE and an SAE can be found in [Appendix 3](#).

AEs will be reported by the participant (or, when appropriate, by a caregiver, surrogate, or the participant's legally authorized representative).

The investigator and any qualified designees are responsible for detecting, documenting, and recording events that meet the definition of an AE or SAE and remain responsible to pursue and obtain adequate information both to determine the outcome and to assess whether it meets the criteria for classification as an SAE or that caused the participant to discontinue the study intervention (see [Section 7](#)).

In addition, the investigator may be requested by Pfizer Safety to obtain specific follow-up information in an expedited fashion.

8.3.1. Time Period and Frequency for Collecting AE and SAE Information

The time period for actively eliciting and collecting AEs and SAEs (“active collection period”) for each participant begins from the time the participant provides informed consent, which is obtained before the participant’s participation in the study (ie, before undergoing any study-related procedure and/or receiving investigational product), through and including a minimum of 28 calendar days after the last administration of the investigational product.

For participants who are screen failures, the active collection period ends when screen failure status is determined.

Medical occurrences that begin before the start of study intervention but after obtaining informed consent will be recorded on the Medical History/Current Medical Conditions section of the case report form (CRF), not the AE section.

Follow-up by the investigator continues throughout and after the active collection period and until the event or its sequelae resolve or stabilize at a level acceptable to the investigator, and Pfizer concurs with that assessment.

Investigators are not obligated to actively seek AE or SAE after conclusion of the study participation. However, if the investigator learns of any SAE, including a death, at any time after a participant has been discharged from the study, and he/she considers the event to be reasonably related to the study intervention or study participation, the investigator must promptly notify the sponsor.

8.3.1.1. Reporting SAEs to Pfizer Safety

All SAEs occurring in a participant during the active collection period are reported to Pfizer Safety on the CT SAE Report Form immediately and under no circumstance should this exceed 24 hours, as indicated in [Appendix 3](#). The investigator will submit any updated SAE data to the sponsor within 24 hours of it being available.

SAEs occurring in a participant after the active collection period has ended are reported to Pfizer Safety if the investigator becomes aware of them; at a minimum, all SAEs that the investigator believes have at least a reasonable possibility of being related to investigational product must be reported to Pfizer Safety.

8.3.1.2. Recording Nonserious AEs and SAEs on the CRF

During the active collection period, both nonserious AEs and SAEs are recorded on the CRF.

8.3.2. Method of Detecting AEs and SAEs

The method of recording, evaluating, and assessing causality of AEs and SAEs and the procedures for completing and transmitting SAE reports are provided in [Appendix 3](#).

Care will be taken not to introduce bias when detecting AEs and/or SAEs. Open-ended and nonleading verbal questioning of the participant is the preferred method to inquire about AE occurrences.

8.3.3. Follow-up of AEs and SAEs

After the initial AE/SAE report, the investigator is required to proactively follow each participant at subsequent visits/contacts. For each event, the investigator must pursue and obtain adequate information until resolution, stabilization, the event is otherwise explained, or the participant is lost to follow-up (as defined in [Section 7.3](#)).

In general, follow-up information will include a description of the event in sufficient detail to allow for a complete medical assessment of the case and independent determination of possible causality. Any information relevant to the event, such as concomitant medications and illnesses, must be provided. In the case of a participant death, a summary of available autopsy findings must be submitted as soon as possible to Pfizer Safety.

Further information on follow-up procedures is given in [Appendix 3](#).

8.3.4. Regulatory Reporting Requirements for SAEs

Prompt notification by the investigator to the sponsor of an SAE is essential so that legal obligations and ethical responsibilities towards the safety of participants and the safety of a study intervention under clinical investigation are met.

The sponsor has a legal responsibility to notify both the local regulatory authority and other regulatory agencies about the safety of a study intervention under clinical investigation. The sponsor will comply with country-specific regulatory requirements relating to safety reporting to the regulatory authority, institutional review boards (IRBs)/ethics committees (ECs), and investigators.

Investigator safety reports must be prepared for suspected unexpected serious adverse reactions (SUSARs) according to local regulatory requirements and sponsor policy and forwarded to investigators as necessary.

An investigator who receives an investigator safety report describing an SAE or other specific safety information (eg, summary or listing of SAEs) from the sponsor will review and then file it along with the investigator's brochure and will notify the IRB/EC, if appropriate according to local requirements.

8.3.5. Exposure During Pregnancy or Breastfeeding, and Occupational Exposure

Exposure to the investigational product under study during pregnancy or breastfeeding and occupational exposure are reportable to Pfizer Safety within 24 hours of investigator awareness.

